## 3.2 Exclusion Criteria

Participants who exhibit any of the following conditions at screening will not be eligible for admission into the study.

CONFIDENTIAL

This document is confidential. Do not disclose or use except as authorized.

3.2.1 Patients < age 18.

3.2.2 Pregnant or breast feeding women.

3.2.3 Previous or current malignancies at other sites, with the exception of adequately treated in situ carcinoma of the cervix, basal or squamous cell carcinoma of the skin, thyroid cancer, prostate cancer treated with surgery/radiotherapy, or other cancer curatively treated by surgery and with no current evidence of disease for at least 5 years.

3.2.4 Other serious illnesses or medical conditions including but not limited to:

- 3.2.4.1 Unstable cardiac disease despite treatment, myocardial infarction within 6 months prior to study entry.
- 3.2.4.2 History of significant neurologic or psychiatric disorders including dementia or seizures
- 3.2.4.3 Active clinically significant uncontrolled infection
- 3.2.4.4 Active peptic ulcer disease defined as unhealed or clinically active
- 3.2.4.6 Active drug addiction including alcohol, cocaine or intravenous drug use defined as occurring within the 6 months preceding diagnosis
- 3.2.4.7 Chronic Obstructive Pulmonary Disease, defined as being associated with a hospitalization for pneumonia or respiratory decompensation within 12 months of diagnosis. This does not include obstruction from tumor
- 3.2.4.8 Autoimmune disease requiring therapy, prior organ transplant, or known HIV infection
- 3.2.4.9 Interstitial lung disease
- 3.2.4.10 Hepatitis C by history
- 3.2.4.11 Concurrent treatment with any other anticancer therapy.
- 3.2.4.12 Participation in an investigational therapeutic drug trial within 30 days of study entry. Participation in additional investigational radiation studies will exclude participation in SIRS. Participation in non-therapeutic, non-oncologic investigational studies (i.e. pain control studies, nutritional studies, etc.) will be allowed amongst SIRS participants, provided there is no alteration of treatment planning, oncologic therapy, or surveillance, and additional studies comply with SIRS safety criteria and stopping rules as outlined in the SIRS protocol.

3.2.5 Advanced Stage III,IV (N2C, N3) or surgically unresectable disease or disease that cannot be fully resected, obvious radiologic ECS, supraclavicular or matted metastatic disease, >3 cervical nodes. (These patients will be placed on the Quarterback trial due to advanced state of disease and poor prognostic features)

3.2.6 p16 or HPV negative OPSCC as determined by IHC and PCR, respectively.

### 3.3 Inclusion of Women, Minorities and Other Underrepresented Populations

CONFIDENTIAL

This document is confidential. Do not disclose or use except as authorized.

The inclusion and exclusion criteria do not affect enrollment of women, minorities, or other under-represented populations.

## **4.0 REGISTRATION PROCEDURES**

After the patient signs the informed consent the patient will be registered for screening and once the investigator has verified that the patient meets all inclusion/exclusion criteria, the patient will be registered for and started on the protocol. Patients who lack p16 and HPV PCR may proceed to surgery however they will not be assigned to an experimental group and registered on the protocol until p16 IHC and HPV PCR are completed and positive. The verification of patient's eligibility and screening completion will be performed centrally after the receipt of the patient primary post-surgical registration form. It is mandatory not to exceed 21 days between the date of registration for screening and the start of the study treatment (surgery). In any case, all events occurring after the registration for therapy must be recorded in the case report form and will be taken into account in the analysis, whether the patient received the study treatment or not. Patient must receive surgery and be p16 IHC and HPV PCR positive to be included in the intent to treat analysis. Patients found to not meet entry criteria will be offered best therapy.

### **4.1 General Guidelines**

Clinicians will register eligible participants with the Clinical Trial Office. Registration must occur prior to the initiation of screening, again prior to therapy, and finally at completion of therapy for assignment. Any participant not registered to the protocol before treatment begins will be considered ineligible and registration will be denied.

A member of the study team will confirm eligibility criteria and complete the protocol-specific eligibility checklist for final registration.

Following registration for therapy, participants will have surgery on study and following surgery re-registration and assignment to treatment group. Issues that would cause treatment delays should be discussed with the Principal Investigator. If a participant does not receive protocol therapy and assignment treatment following registration, the participant's protocol status must be changed to registered not treated. Notify the registrar of participant status changes as soon as possible. Patients who are eligible and do not receive study surgery will be analyzed in a separate cohort.

### **4.2 Registration Process**

The registration procedures are as follows:

1. Obtain written informed consent from the participant prior to the performance of any study related screening procedures or assessments and register consent and register the patient for screening.
2. Complete the protocol-specific screening and eligibility checklist using the eligibility assessment documented in the participant's medical/research record. To be eligible for registration to the surgery on study, the participant must meet each inclusion and exclusion criteria listed on the eligibility checklist, however p16 and HPV PCR results need not be necessary.
3. Patients will be re-registered for post-surgical adjuvant treatment assignment as per the protocol design and will require final p16 IHC and HPV PCR for this. Pathologic criteria as outlined in the protocol will determine the post-surgical adjuvant arm assignment.

**CONFIDENTIAL**

This document is confidential. Do not disclose or use except as authorized.

Reminder: Confirm eligibility for ancillary studies at the same time as eligibility for the treatment study. Registration to both treatment and ancillary studies will not be completed if eligibility requirements are not met for all studies.

## 5.0 TREATMENT PLAN

### Determination of Stage

Clinical stage will be based on clinical exam, and office based endoscopic evaluation with flexible endoscopy of the upper aerodigestive tract as well as radiographic evaluation with CT and/or MRI in conjunction with CT/PET. Formal operative endoscopy with biopsy under general anesthesia will be performed as indicated when diagnostic or staging dilemma occurs. A preoperative tissue biopsy will be taken and used for histopathological analysis and assignment of p16 status and, if possible, HPV status. All biopsies performed outside the institution will be internally reviewed by pathology department according to protocol guidelines and repeat biopsies will be obtained if there is inadequate tissue for analysis. All patients will be presented and reviewed at multidisciplinary tumor board. Final staging will be performed according to standard 8th Edition AJCC TNM criteria.

### Surgical Intervention

Patients who meet inclusion criteria and are surgical candidates will be consented for primary surgical therapy. Surgery will include transoral robotic resection of the tumor with negative intraoperative frozen section margins. Selective neck dissection of levels II-IV will be performed routinely ipsilateral to the primary tonsillar tumors. Bilateral selective neck dissection of levels II-IV will be performed for all tongue base tumors. Additional levels (i.e. I, V) will be performed at the discretion of the operating surgeon if indicated on the size and location of the primary tumor. Appropriate reconstruction will be performed at the time of tumor resection as deemed necessary by the operating surgeon.

### Pathological Evaluation/Criteria and Post-Operative Treatment Assignments

#### Group I:

- Complete resection (margins: tonsil >1mm, tongue >3mm, pT1-2, pN0-2B),
- No LVI, no PNI, <3 positive nodes.
- No ECS, No matted or Level  $\geq$ III,

#### Group I Protocol

- No adjuvant therapy
- Clinical evaluations every 3-4 months the first year

PET or CT at 4 months, 12 months, 24 months, 36 months 48 54, and 60 months unless clinically indicated

#### Group II

- Complete resection (margins: tonsil <1mm, tongue <1mm, pT1-2, pN0-2B),
- +LVI, +PNI, <3 positive nodes, or  $\leq$ 1mm ECS.

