#### Group IIIA

- $\geq 3$  nodes (without ECS  $\geq 1\text{mm}$ )
- +Supraclavicular nodes (without ECS  $\geq 1\text{mm}$ )
- +Contralateral nodes (without ECS  $\geq 1\text{mm}$ )

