#### Group IIIB

- Incomplete surgical resection with +surgical margins
- $\geq 1\text{mm}$  ECS or matted nodes
- $> 6 +$  nodes

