#### Group IIIB Protocol

- CCRT with cisplatin and 5600 cGy
- Monthly clinical evaluation first year,

PET or CT at 4 months, 12 months, 24 months. 36 months 48 54, and 60 months unless clinically indicated

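### The visible post-operative assignment criteria give some pathology results two groups, leave others unnamed in Group II, and state no 56 Gy volume for some Group IIIB patients

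*Combined protocol and SAP*

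**What the plan says.** Section 4.2 states: "Pathologic criteria as outlined in the protocol will determine the post-surgical adjuvant arm assignment". The visible text gives no order of precedence and no default group. The criteria and treatments in Section 5.0 are:

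- **Group I (no adjuvant therapy):** "Complete resection (margins: tonsil >1mm, tongue >3mm, pT1-2, pN0-2B"; no LVI, no PNI and fewer than three positive nodes; then "No ECS, No matted or Level" III or beyond.
- **Group II (50 Gy, no chemotherapy):** "Complete resection (margins: tonsil <1mm, tongue <1mm, pT1-2, pN0-2B"; then, on a second line, "LVI, +PNI, <3 positive nodes, or" ECS of at most 1 mm. How the two lines combine is not stated.
- **Group IIIA (cisplatin and 50 Gy):** three or more nodes, supraclavicular nodes or contralateral nodes. Each is qualified by "nodes (without ECS" of 1 mm or more. The node count has no upper limit.
- **Group IIIB:** positive margins; 1 mm or more of "ECS or matted nodes"; or more than six positive nodes. Treatment is "CCRT with cisplatin and 5600 cGy".

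The Group IIIB target-volume text ties CTV56 to two findings: a positive margin (tumor bed) and ECS greater than 1 mm (bed of that node). It lists the tumor bed with a negative margin, and nodal regions without ECS, under CTV50.4. Target Dose Prescriptions gives Group IIIB 56 Gy in 2.0 Gy fractions and 50.4 Gy in 1.8 Gy fractions, with no exception by reason for assignment. The Pathology Review Checklist records ECS as below, equal to or above 1 mm. Its node-location item names supraclavicular and ipsilateral or contralateral site, but not node level or matting.

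**The concern.** In a de-escalation trial the assignment rule is part of the intervention, so it should give each resected patient exactly one group. Here two investigators applying the text faithfully could treat the same pathology report differently. The widest contrast is at ECS of exactly 1 mm: radiotherapy alone or cisplatin chemoradiotherapy. For some Group IIIB patients the planner also has to choose the boost volume without a written criterion. The results are to be reported by pathologic group (Section 16.3), so inconsistent placement would also blur what each adjuvant group represents.

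**Working it through.** The plan gives no figure to reproduce. The check applies the written criteria to specific pathology results. Unless the row says otherwise, each has a complete resection with Group I margins, pT1-2, fewer than three ipsilateral Level II nodes and no other adverse feature.

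| Result | I | II | IIIA | IIIB |
|---|---|---|---|---|
| ECS exactly 1 mm, close margin | no | yes | no | yes |
| ECS exactly 1 mm, Group I margin | no | only if one feature suffices | no | yes |
| 7 nodes, no ECS | no | no | yes | yes |
| 3 matted nodes, no ECS | no | no | yes | yes |
| 3 nodes, positive margin, no ECS | no | no | yes | yes |
| Tongue margin 2 mm | no | not named | no | no |
| Tonsil margin exactly 1 mm | no | not named | no | no |
| One ipsilateral Level III node | no | not named | no | no |

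**(a) The 1 mm boundary.** Group II includes 1 mm and Group IIIB also includes it. With a close margin the overlap exists however Group II's two lines are joined. With a Group I margin it exists only if a single risk feature is enough for Group II. CTV56 uses strictly more than 1 mm, while CTV50.4 takes nodal regions with no ECS. The bed of a node with exactly 1 mm is therefore named in neither volume, even if the patient is placed in IIIB.

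**(b) IIIA and IIIB.** Without a ceiling, three or more includes more than six. Matted nodes or a positive margin with three or more nodes creates the same overlap.

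**(c) Groups I and II.** The last three rows could enter Group II only if its final connector is read so that fewer than three nodes qualifies alone. That reading would also put every Group I patient in Group II, so it cannot be intended.

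**(d) CTV56.** A patient in IIIB only for more than six nodes or matted nodes, with negative margins and no ECS, meets neither CTV56 condition. Both the tumor bed and the nodal regions are listed under CTV50.4.

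**Dose contrasts, from the protocol's prescriptions:**

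- Fractions: 50 / 2.0 = 25; 56 / 2.0 = 28; 50.4 / 1.8 = 28.
- Cisplatin over 28 fractions: 28 / 5 = 5.6 weeks, so 5-6 doses of 40 mg/m², or 200-240 mg/m².
- (a) 50 Gy in 25 fractions without cisplatin, or 56 Gy in 28 fractions with 200-240 mg/m².
- (b) With a positive margin, the tumor bed receives 50 or 56 Gy, a difference of 6 Gy; both groups receive cisplatin. For more than six nodes or matted nodes the contrast depends on (d): taken literally, the volumes give 50 against 50.4 Gy.
- (d) 56 - 50.4 = 5.6 Gy, both in 28 fractions.

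**The case against.** Much of this can be answered from the document.

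- Group I is a closed list, and only Group I receives no adjuvant therapy. Section 1.0 sends early-stage disease as defined to surveillance and intermediate-risk patients to 50 Gy. A patient who fails Group I and has no Group III feature therefore belongs in Group II.
- Section 2.2 describes more than six nodes as marking more advanced disease and refers to Groups IIIA and IIIB. A separate line for it in IIIB has no purpose unless it overrides IIIA.
- The Section 1.3 schema is not visible and may state an order or further criteria.
- Exactly 1 mm is a boundary value. Matted nodes and more than three nodes are excluded at entry (Sections 3.1.2 and 3.2.5), so these cases arise through pathologic upstaging.
- A non-treating radiation oncologist reviews every plan, and Appendix 4 adds central volume review for the participating site.

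Most of this stands, and it lowers the weight of (b) and (c). It does not resolve the two 1 mm rules, and the checklist makes exactly 1 mm a recordable result. The case for IIIB in Section 2.2 covers node count, not matted nodes or a positive margin with three or more nodes. Plan review is a real safeguard, but the reviewer has no written CTV56 criterion for the patients in (d).

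A reader might infer that the gap in (c) decides who enters the surgery-alone cohort behind objectives 1.1.1-1.1.3 and the Group 1 sample of 100. The documents do not support this. These patients plainly fail Group I; what is missing is their mention in Group II.

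**Conclusion.** The concern holds as a conflict and incompleteness in the visible assignment and target-volume text, and it should be fixed. The firmest parts are (a), where one recordable result leads to radiotherapy alone or to chemoradiotherapy, and (d), where 56 Gy is prescribed without a stated volume. In (b) precedence is missing, although IIIB is clearly indicated for more than six nodes. In (c) Group II needs completing, and Group I membership is not seriously in doubt.

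The documents give no frequencies, and the number of patients affected is probably low. The conclusion rests on the visible text: the Section 1.3 schema might supply an order or some of the missing criteria. Nothing here calls the Group 1 sample size into question.

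**What to change.** 1. Use one 1 mm inequality in Groups II, IIIA and IIIB and in the CTV56 text. The smallest change is below 1 mm for Group II and 1 mm or more for IIIB and CTV56, which edits only the Group II and CTV56 wording. The alternative, at most 1 mm for II and IIIA and above 1 mm for IIIB and CTV56, would move exactly 1 mm with 3-6 nodes from IIIB to IIIA.
2. Limit the IIIA node-count rule to 3-6 nodes.
3. State that groups are applied in the order IIIB, IIIA, II, I.
4. Restate Group II as complete resection, fewer than three nodes, no Group III feature, and any one of: a margin not meeting Group I, LVI, PNI, ECS below the cut-off, or an ipsilateral node at Level III or beyond.
5. State that CTV56 covers the involved nodal bed when IIIB is assigned for more than six nodes or matted nodes, or state explicitly that these patients receive 50.4 Gy only. The radiation oncology investigators should confirm which.
6. Add node level and matted status to the Pathology Review Checklist.

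With the smallest change in item 1, the first five rows of the table go to IIIB alone and the last three to Group II alone.

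The cost is amendment wording and two checklist fields. The cut-off, the Group II additions and CTV56 need a decision by the surgical and radiation oncology investigators. No new tests or patients are needed.

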#### Group II Protocol

- Postoperative XRT 5000 cGy

CONFIDENTIAL

This document is confidential. Do not disclose or use except as authorized.

- Clinical evaluations every 3-4months during the first year
- PET or CT at 4 months, , 12 months, 24 months. 36 months 48 54, 60 unless clinically indicated. (Newer data suggests we can substitute quarterly cfDNA after initial clear PET through year 2 and then q 6 months through year 4 and then yearly through year 6. Physicians have the option to follow with cfDNA in all groups, but with imaging, as indicated).

#### Group IIIA

- $\geq 3$  nodes (without ECS  $\geq 1\text{mm}$ )
- +Supraclavicular nodes (without ECS  $\geq 1\text{mm}$ )
- +Contralateral nodes (without ECS  $\geq 1\text{mm}$ )

#### Group IIIA Protocol

- CCRT with cisplatin and 5000 cGy
- Monthly clinical evaluation first year,

PET or CT at 4 months, 12 months, 24 months. 36 months 48 54, and 60 months unless clinically indicated.

#### Group IIIB

- Incomplete surgical resection with +surgical margins
- $\geq 1\text{mm}$  ECS or matted nodes
- $> 6 +$  nodes

#### Group IIIB Protocol

- CCRT with cisplatin and 5600 cGy
- Monthly clinical evaluation first year,

PET or CT at 4 months, 12 months, 24 months. 36 months 48 54, and 60 months unless clinically indicated

## PATHOLOGY REVIEW CHECKLIST

1. Primary OPSCC, location
2. Histologic differentiation (H/E)
3. HPV + PCR
4. p16+
5. Margin status in mm
6. PNI
7. LVI
8. ECS  $< = > 1\text{mm}$
9. Number of cervical metastatic nodes
10. Location of involved nodes (i.e., supraclavicular, ipsilateral vs. contralateral)
11. pAJCC staging

## DELIVERY OF RADIATION (XRT)

All patients will receive daily radiation treatment with intensity-modulated radiotherapy (IMRT). Treatment will be given 5 days per week and, as per standard practice, will not be delivered on Saturday, Sunday or major holidays. Radiotherapy will be administered according to the guidelines below:

### Technical Factors

CONFIDENTIAL

This document is confidential. Do not disclose or use except as authorized.

Photon beams of  $\geq 4$  MV are required. Intensity Modulated Radiotherapy (IMRT) is required for all cases. IMRT via dynamically moving leaves, step-and-shoot with a multileaf collimator, Rapid Arc, binary multileaf collimator and tomotherapy are allowed. Three-dimensional conformal radiotherapy (3D-CRT) and proton therapy are not allowed.

### **Immobilization, Simulation, and Localization**

A thermoplastic head mask (or similar immobilization device) is required for IMRT. Bite blocks, dental rolls and other set-up techniques may be used at the discretion of the treating radiation oncologist. A treatment planning CT scan is mandatory for defining target volumes. IV contrast is not required for the treatment planning CT. CT scan thickness should be  $\leq 0.3$  cm. The treatment planning CT scan should be acquired with the patient in the same position and using the same immobilization device as for treatment. Volumes for all structures must be contoured on each relevant CT slice.

### **Treatment Planning/Target Volumes**

#### **Gross Tumor Volume (GTV)**

Since radiotherapy will be given postoperatively there should not be any gross disease and therefore no GTV.

#### **Clinical Target Volume (CTV) – Group II and IIIA**

The clinical target volume (CTV) is generated to account for microscopic disease. CTV50 may include the primary tumor bed and/or lymph node regions in the neck at risk for harboring microscopic disease. CTV50 should not include bone or air. There will be only one CTV (CTV50) for patients in Group II and IIIA.

#### **Clinical Target Volume (CTV) – Group IIIB**

CTV56 is generated to account for areas at highest risk of harboring microscopic disease (positive margin or positive ECS  $> 1$  mm). If there is a positive margin, CTV56 should encompass the primary tumor bed. If there is extracapsular spread  $> 1$  mm, CTV56 should encompass the operative bed of the lymph node that was found to have ECS. Group IIIB will have a second CTV, called CTV50.4. CTV50.4 is generated to account for areas at lower risk for harboring microscopic disease than CTV56. CTV50.4 may include the primary tumor bed (if negative margin) and/or lymph node regions (if no ECS) in the neck. CTV56 and CTV50.4 should not include bone or air. There are 2 CTVs for the Group IIIB(CTV56 and CTV50) which will be treated with a simultaneous integrated boost (SIB) technique.

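### ECS of exactly 1 mm meets the criteria for both Group II and Group IIIB, and patients in IIIB only for matted nodes or more than 6 nodes have no stated site for the required 56 Gy volume

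*Combined protocol and SAP*

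**What the plan says.** All references are to Section 5.0 of the combined protocol and SAP unless stated.

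**Assignment.** Group II requires a complete resection and lists "LVI, +PNI, <3 positive nodes, or" ECS of 1 mm or less. Its treatment is "Postoperative XRT 5000 cGy", with no chemotherapy. Group IIIA takes 3 or more nodes, or supraclavicular or contralateral nodes, in each case without ECS of 1 mm or more. Its treatment is "CCRT with cisplatin and 5000 cGy". Group IIIB takes positive margins, ECS of 1 mm or more, matted nodes, or more than 6 positive nodes, and gives cisplatin with 5600 cGy.

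**Volumes for Group IIIB.** The text is explicit that "There are 2 CTVs for the Group IIIB", and Target Dose Prescriptions sets 56 Gy for PTV56 and 50.4 Gy for PTV50.4. The high-dose volume is defined as follows: "CTV56 is generated to account for areas at highest risk of harboring microscopic disease (positive margin or positive ECS" above 1 mm. Two locations are given. The first is "If there is a positive margin, CTV56 should encompass the primary tumor bed". The second, for ECS above 1 mm, is the bed of the node that showed it. For the lower-dose volume, "CTV50.4 may include the primary tumor bed (if negative margin) and/or lymph node regions (if no ECS) in the neck".

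**Recording.** The Pathology Review Checklist records ECS as below, equal to or above 1 mm, together with margin and node count. It has no item for matted nodes.

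**The concern.** There are two separate faults.

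First, the criteria for Group II and Group IIIB both include the value 1 mm, and the CTV56 rule excludes it. Two clinicians who follow the protocol exactly could give the same patient radiotherapy alone at 50 Gy or chemoradiotherapy at 56 Gy. Because the checklist has a category for exactly 1 mm, the case can be recorded and must then be assigned.

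Second, Group IIIB admits patients by routes that the CTV56 rule does not cover. A plan with 50.4 Gy only would breach the protocol. A plan with 56 Gy has no written site when matted nodes or more than 6 nodes is the only reason for being in the group.

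What is at stake is consistent treatment of patients with the same pathology, and an accurate account of what the de-intensified regimen was.

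**Working it through.** **Dose arithmetic (Target Dose Prescriptions; Section 5.1).**
- Group IIIB: 56 / 2.0 = 28 fractions, and 50.4 / 1.8 = 28 fractions. The two IIIB doses fit one simultaneous integrated boost schedule, so the stated doses reproduce.
- Groups II and IIIA: 50 / 2.0 = 25 fractions.
- Difference between IIIB and the 50 Gy groups: 56 − 50 = 6 Gy.
- Cisplatin is 40 mg/m² weekly. Twenty-eight fractions at 5 per week take 28 / 5 = 5.6 treatment weeks. The number of doses is not stated; assuming 5 to 6, the total is 5 × 40 = 200 to 6 × 40 = 240 mg/m².

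**Rules applied to example patients.** Other adverse features are taken as absent, and resection is complete except in the first row.

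| Pathology | Groups whose criteria are met | Stated CTV56 site | Named for CTV50.4 |
|---|---|---|---|
| Positive margin, no ECS | IIIB | Primary bed | Nodal regions |
| ECS 2 mm, 2 nodes | IIIB | Bed of that node | Primary bed |
| ECS exactly 1 mm, 2 nodes | II and IIIB | None | Primary bed only |
| Matted, 2 nodes, no ECS | IIIB | None | Primary bed, nodal regions |
| 7 nodes, no ECS | IIIA and IIIB | None | Primary bed, nodal regions |

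**Reading the third row.** In Group II the patient receives 50 Gy and no cisplatin. In Group IIIB the patient receives 56 Gy with about 200 to 240 mg/m² of cisplatin, on the assumption above. In IIIB, the bed of the affected node falls between the two volumes: CTV56 needs more than 1 mm, and CTV50.4 mentions nodal regions only where there is no ECS.

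No choice of group satisfies all three rules. Choosing IIIB overrides the equality in the Group II criterion and leaves CTV56 without a site. Choosing II overrides the equality in the IIIB criterion. The Group II and CTV56 rules agree with each other (the division lies above 1 mm). The IIIA and IIIB criteria agree with each other (the division lies at 1 mm).

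**Reading the last two rows.** With the IIIB routes split into positive margin, ECS above 1 mm, ECS of exactly 1 mm, matted nodes and more than 6 nodes, the last three of the five have no CTV56 site when neither of the first two is present.

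**The case against.** The best reply is that clinical judgement and review fill these gaps, and much of it stands.

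- **Review before treatment.** Under Quality Assurance, a radiation oncologist who is not treating the patient reviews each plan first. Appendix 4 adds volume review by the coordinating center for the participating site, and all patients go to tumor board. This reduces inconsistency, but the reviewers have no written standard for these patients and cannot reconcile two conflicting inequalities.
- **Permissive volume text.** A reader might infer that the protocol forbids 56 Gy to a margin-negative primary bed or an ECS-free nodal bed. It does not: CTV50.4 only may include those regions. A planner could treat a matted-node bed as an area of highest risk, and that is the natural reading. It is still not written, and the parenthesis defining CTV56 names only margin and ECS.
- **More than 6 nodes.** A reader might infer that the dose for 7 ECS-free nodes is unsettled because Group IIIA has no upper limit. That goes too far. If IIIA took these patients, the separate criterion would do nothing for anyone without another IIIB feature, so the natural reading is IIIB. Only the missing CTV56 site remains.
- **Missing figure.** The treatment schema in Section 1.3 is not available here and might show an order of precedence. That could settle which group applies, but it would not supply the missing volume rules.
- **Few patients.** Section 3.2 excludes matted disease, more than 3 cervical nodes and obvious radiologic ECS at screening, so these cases arise only as unexpected surgical pathology. This is right, and it is why the point is minor.

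**Conclusion.** Wrong as written, and minor. At exactly 1 mm of ECS with fewer than 3 nodes, the plan's explicit rules give two incompatible treatments: 50 Gy alone, or 56 Gy with weekly cisplatin. This is a conflict between stated rules, not missing detail. In addition, patients in Group IIIB only for matted nodes or more than 6 nodes must have a 56 Gy volume for which no site is stated.

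The number affected is not given and is probably small. A reader might infer damage to the trial's hypotheses, but the documents do not support that. Section 16.1 states the adjuvant hypotheses for Groups 2 and 3 together, and the sample size in Section 16.2 concerns Group I, which receives no radiotherapy. The consequence is for consistent treatment and accurate description of the regimen.

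The conclusion rests on the current text of Section 5.0. The cisplatin total rests on the assumed 5 to 6 doses. If the unseen schema gives precedence between groups, the assignment conflict could be resolved, but the gap in the volume rules would remain.

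**What to change.** 1. **Use one ECS cut-off throughout.** Changing the Group IIIA and IIIB criteria to more than 1 mm is the smallest edit, because Group II and the CTV56 rule already agree with it. ECS of exactly 1 mm without other features then goes to Group II (50 Gy, no cisplatin). This is a treatment decision, so the sponsor's radiation and medical oncologists should confirm it. If they prefer 1 mm or more, edit Group II and the CTV56 rule instead; these patients then stay in IIIB, with that node's bed in CTV56. Either way, replace the no-ECS condition for CTV50.4 with the same cut-off.
2. **Give CTV56 a site for the remaining IIIB routes.** State that it covers the operative bed of matted nodes and, for more than 6 nodes, the involved nodal bed. If 56 Gy was not intended for patients with more than 6 nodes and nothing else, move them to Group IIIA at 5000 cGy.
3. **Optional clarification.** If these patients stay in IIIB, write 3 to 6 nodes in Group IIIA.

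The cost is one amendment with short edits to Section 5.0, and no extra patients, visits or procedures. Matted status can be inferred by elimination: a IIIB patient with a negative margin, ECS below the cut-off and no more than 6 nodes can be there for no other reason. Adding it to the pathology checklist as one item would be cleaner.
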